### 3.2 Study Endpoints

The primary analysis objective in this pilot study is to estimate response magnitude and variation in esophageal inflammation and injury in BE as measured by tissue PGE2, the esophageal inflammation score, esophageal macrophage infiltration and modulation of esophageal macrophage phenotype attributable to  $\omega$ 3 FFA supplementation. This will be the information needed to design a larger adequately powered study to study the efficacy of  $\omega$ 3 FFA as a chemoprevention agent in BE.

**Aim 1:** The **primary response** outcome is tissue PGE2 levels and the main secondary response outcome is the histologic score of 3 or 4 (severe grades of inflammation). Other **secondary outcomes** include pre and post supplementation serum and tissue  $\omega$ 3 FFA levels.

**Aim 2:** The **primary response** outcome is the cytokine expression profile in esophageal biopsies as measured by qPCR [IL1 $\beta$ , IL6 (M1 markers) versus IL1, IL10 (M2 markers)]. **Secondary response outcomes** include change in esophageal macrophage counts and phenotype proportions (total, %M1, %M2).

**Aim 3:** The primary response outcome is change in esophageal mucosal impedance (baseline-post treatment) which is a physiologic correlate of the epithelial barrier function, with  $\omega$ 3 FFA supplementation. Secondary outcomes include the association of esophageal mucosal impedance with measures of central obesity (waist circumference, waist hip ratio and abdominal visceral fat area on CT) at baseline and following treatment.

**Aim 4:** The primary response outcome is the change in the esophageal microbiome in BE subjects following  $\omega$ 3 FFA supplementation. Secondary outcomes will be the association of the microbiome pattern with measures of central obesity ((waist circumference, waist hip ratio and abdominal visceral fat area on CT).

Assays performed at baseline and at 6 months will include:

*Aim 1:* Primary outcome: Tissue PGE2 in esophageal biopsies. This will be performed by previously described methods [21] on esophageal biopsies snap frozen at -80^0 C in [name] laboratory.

Secondary outcomes: 1. Tissue inflammation score (grade 0-3). This will be performed on esophageal H&E stained sections as previously described [5], by [name], an experienced gastrointestinal pathologist. 2. Esophageal tissue EPA levels: this will be performed on esophageal biopsies obtained at baseline and at 6 months, in the Metabolomics Core laboratory. 3. Serum  $\omega$ 3 FFA levels: will be performed using mass spectroscopy/liquid chromatography in the Immunochemistry Core laboratory at baseline and 6 months.

*Aim 2:* Primary outcome: 1. Quantification of esophageal macrophage infiltration (and subtypes) by qPCR for CD68 (macrophage marker) TNF $\alpha$  and MCP1 (M1 markers) and CD206, IL1, IL10, as M2 markers). This will be performed in collaboration with [name] (see preliminary data and letter of support) using previously described standard methodology [29].

Secondary outcomes : Esophageal macrophage counts (using CD68 and HAM 56 as markers) and proportion of M1 and M2 (CD206) using immunofluorescence will be performed using previously described methods [24]. Cells double labeled for CD206 and CD68 will be categorized as M2 cells and those staining only with CD68 will be categorized as M1 cells. Cell counts will be performed as previously described.

Aim 3: Esophageal mucosal impedance measurements will be obtained using a esophageal mucosal impedance catheter at 2 cm, 5 cm and 7 cm above the GEJ. At least one measurement will be obtained in the squamous mucosa at 3 cm above the BE segment [30].

Aim 4: The esophageal microbiome will be characterized from biopsies and brushings from the squamous and columnar epithelium using standard methods.

Sequencing : Biopsy samples and brushings will be collected in cryo-vials and flash frozen in liquid nitrogen. All samples will be stored at -80 till they are ready for processing.

Next Generation sequencing:

Bacterial DNA will be enriched in biopsy and brushings using NEBNext microbiome DNA enrichment kit if concentrations are low. Amplicons spanning the variable region 4 (V4) of bacterial 16SrRNA will be generated using a barcoded reverse primer (515F, 806R). Samples will be sequenced using the MiSeq platform at Mayo Genome Facility to obtain 300bp paired end reads. Based on our previous experience we will sequence at most 100 samples in one sequencing run and we expect ~30,000 high quality reads per sample.

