*Anti-inflammatory effects of  $\omega$ 3 FFA:* Increased intake of polyunsaturated FFAs and  $\omega$ 3 FFAs in particular, is associated with a 50% lower risk of BE [17].  $\omega$ 3 FFAs have been shown to have anti-neoplastic activity in the colon. *A major proposed mechanism by which  $\omega$ 3 FFAs exert anti-inflammatory and antineoplastic effect is by modulation of prostaglandin biosynthesis, by providing an alternate substrate for COX-2 (instead of the  $\omega$ 6 FFA : Arachidonic acid), which leads to decreased PGE2 production, epithelial proliferation and adenoma/aberrant crypt foci number in animal and human trials [9] [18-20]. We have shown in prior studies that increased levels of COX2 are seen with increasing grades of dysplasia in BE and that inhibition of COX-2 activity leads to reduced EAC incidence in an animal model of BE, by reducing PGE2 production [21, 22].  $\omega$ 3FFAs have also been shown to modulate macrophage phenotype from proinflammatory (M1) to anti-inflammatory (M2). GPR120 has been identified as a likely  $\omega$ 3FFA receptor, mediating the anti-inflammatory and insulin sensitizing effects of  $\omega$ 3FFAs on macrophages and tissue [13]. Our novel central hypothesis is that *oral supplementation with  $\omega$ 3 FFAs in obese BE subjects will lead to downregulation of pro-neoplastic inflammatory pathways in BE by modulating the esophageal macrophage phenotype from proinflammatory to anti-inflammatory.* We propose to test this hypothesis by the following specific aims, using a randomized controlled trial study design:*

Specific Aim 1: To estimate the magnitude and variation of changes in esophageal inflammation and injury in BE as measured by tissue PGE2 and the esophageal inflammation score, attributable to  $\omega$ 3 FFA supplementation.

Specific Aim 2: To estimate the magnitude and variation of changes in esophageal macrophage infiltration and modulation of esophageal macrophage phenotype attributable to  $\omega$ 3 FFA supplementation.

Specific Aim 3: To estimate the magnitude and variation in changes in esophageal mucosal impedance attributable to  $\omega$ 3 FFA supplementation.

Specific Aim 4: To define the baseline esophageal mucosal microbiome and the potential change in the esophageal mucosal microbiome attributable to  $\omega$ 3 FFA supplementation.

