**Pitfalls and Alternative approaches:** It is possible that recruitment to this trial may be challenging. However, more than 400 patients with BE are seen annually in Rochester and the PI has successfully led and participated in many prospective studies which have recruited BE patients for clinical trials. It also possible, though unlikely, that the in-vitro effects of  $\omega$ 3 FFAs may not translate into clinical effects in terms of alterations in tissue PGE2 and macrophage counts. We will also consider assessing the influence of  $\omega$ 3 FFA on BE cell survival, a known biological correlate to neoplastic progression in BE, using Ki-67-Caspase dual staining to assess other biologic effects of  $\omega$ 3 FFA. Concomitant ASA use may confound the effects on PGE2 levels. Given that this is a preliminary study, we will collect data on ASA and NSAID use and perform analysis stratified on ASA and NSAID use. The randomized study design will however mitigate this confounding effect to a large extent. It is possible that the dose of  $\omega$ 3 FFA used in this proposal may be inadequate for a clinical effect in vivo. We have chosen the 3.6 grams/day dose as described in prior human clinical trials: this dose has been shown to be well tolerated and able to produce meaningful clinical response in human trials. We also have proposed to target subjects with a BMI>30 given that these subjects with increased visceral fat are most likely to benefit from  $\omega$ 3 FFAs.

**Feasibility and Timeline:** We anticipate recruitment to be complete in 6-9 months following IRB approval (which has been initiated). Assays and analysis should be completed in 3 months following completion of the trial and publication thereafter. Assays have been previously performed and validated in multiple published manuscripts by collaborators and Core laboratories. Preliminary data obtained from this trial will be crucial in supporting an aim of a R01 application focused on assessing the mechanistic relationship between BE and central obesity.

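### Section 3.2 gives conflicting sets of primary outcomes and ranks none across aims, so which measure leads the report, or sizes the next trial, is left open

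*Combined protocol and SAP*

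**What the plan says.** Section 3.2 opens with the overall objective: "The primary analysis objective in this pilot study is to estimate response magnitude and variation in esophageal inflammation and injury in BE". The measures it names are tissue PGE2 and then "the esophageal inflammation score, esophageal macrophage infiltration and modulation of esophageal macrophage phenotype attributable to" the supplement.

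The aim paragraphs that follow assign ranks differently:

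- Aim 1: PGE2 is primary, and "the main secondary response outcome is the histologic score of 3 or 4 (severe grades of inflammation".
- Aim 2: the qPCR cytokine profile is primary. Secondary outcomes "include change in esophageal macrophage counts and phenotype proportions (total, %M1, %M2".
- For impedance, under Aim 3: "The primary response outcome is change in esophageal mucosal impedance (baseline-post treatment".
- For the microbiome, under Aim 4: "The primary response outcome is the change in the esophageal microbiome in BE subjects".

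The assay list later in Section 3.2 defines the Aim 2 primary again, as macrophage infiltration and subtypes by qPCR, using other markers. Section 7.1 restates the estimation objective without naming a measure. It repeats the primary and secondary labels for Aims 1 and 2 only, and plans 95% confidence intervals for arm differences across the response data. No section orders the outcomes across aims.

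**The concern.** The pilot is meant to supply the numbers for a larger chemoprevention trial and to support a grant application. That purpose needs one agreed quantity whose estimate is reported first, whatever it shows. As written, an author could cite Section 3.2 in support of leading with PGE2, the inflammation score, a macrophage measure, impedance or the microbiome. If the choice is made after the data are seen, the measure that looks best is likely to be the one put forward. Its estimate is then biased upward because of how it was chosen, and a trial sized on it would be too small. No significance test is needed for this to happen.

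**Working it through.** **Step 1. Status of each measure, place by place.**

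| Measure | Objective sentence, 3.2 | Aim paragraphs, 3.2 | Assay list, 3.2 | Section 7.1 |
|---|---|---|---|---|
| Tissue PGE2 | listed | primary (Aim 1) | primary | primary |
| Inflammation score | listed | main secondary (Aim 1) | secondary | main secondary |
| Macrophage infiltration and phenotype | listed | counts and proportions secondary (Aim 2) | by qPCR primary; by cell staining secondary | counts and proportions secondary |
| qPCR cytokine profile | not named | primary (Aim 2) | qPCR primary, other markers | primary |
| Impedance change | absent | primary (Aim 3) | described, not ranked | analysed, not called primary |
| Microbiome change | absent | primary (Aim 4) | described, not ranked | analysed, not called primary |

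PGE2 is the only row that is clearly primary in both the objective sentence and the aim paragraphs. The inflammation score is the unambiguous case of a secondary measure placed in the primary objective. The macrophage measures have a mixed status.

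**Step 2. The two definitions of the Aim 2 primary.**

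- Aim paragraph and Section 7.1: IL1β and IL6 as M1 markers; IL1 and IL10 as M2 markers.
- Assay list: CD68 for macrophages overall; TNFα and MCP1 as M1 markers; CD206, IL1 and IL10 as M2 markers.

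The lists share IL1 and IL10. They have no M1 marker in common.

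**Step 3. Illustration: chance that at least one of four looks positive.** The plan gives no figure to reproduce; Section 7.1 states no power, effect size or alpha for Aims 1 to 3. Assumptions of this review: no true effect, each aim-level primary read once at two-sided 5% (or its 95% interval read against zero), and a common correlation ρ.

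- ρ = 0: 1 − 0.95⁴ = 1 − 0.8145 = 18.5%.
- ρ > 0: 1 − ∫ φ(u) [Φ((1.96 − √ρ·u)/√(1−ρ)) − Φ((−1.96 − √ρ·u)/√(1−ρ))]⁴ du, which gives 15.6% at ρ = 0.5 and 11.4% at ρ = 0.8.
- Upper bound for any dependence: 4 × 5% = 20%.

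**Step 4. Illustration: size of the selection bias.** Input: 40 per arm (Section 3.1). The standard error of a standardized arm difference is √(2/40) = 0.224 SD. The expected maximum of four independent standard normal variables is 1.029; with common correlation ρ it is multiplied by √(1−ρ). With no true effect, the average apparent effect of the most favourable of four is:

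- ρ = 0: 0.224 × 1.029 = 0.23 SD.
- ρ = 0.5: 0.224 × 1.029 × 0.707 = 0.16 SD.
- ρ = 0.8: 0.224 × 1.029 × 0.447 = 0.10 SD.

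A contrast named in advance has no such bias. Its 95% interval at 40 per arm has half-width t(0.975; 78 df) × √(2/40) = 0.445 SD, so the selection bias is roughly a quarter to a half of that half-width (0.10/0.445 = 0.23; 0.23/0.445 = 0.52).

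**The case against.** The strongest reply is that this is an estimation pilot. Section 2 words Aims 1 to 3 as estimating magnitude and variation, and Section 7.1 plans summaries and intervals. No decision about success is planned, so none can be corrupted, and the rates in Step 3 are not properties of this design. That stands. A reader might infer from the four primaries that the trial breaches a 5% error limit, or that the pilot lacks a deciding test it was supposed to have; the documents support neither reading.

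The reply does not remove the point. Section 1.1 introduces the aims with "We propose to test this hypothesis by the following specific aims". Section 7.1 plans an unspecified test of impedance change and a 0.05 threshold in the microbiome analysis, where the false-discovery correction covers individual taxa only. Estimation for planning also needs a designated quantity.

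Three further readings go too far:

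- *All the macrophage measures are secondary.* The assay list makes infiltration and subtypes by qPCR the Aim 2 primary; only the staining-based counts and proportions are secondary there.
- *Section 7.1 repeats four primaries.* It uses that label for Aims 1 and 2 only.
- *Ki-67/caspase staining is a fallback for a null result.* The text says "We will also consider assessing the influence of" the supplement on cell survival. It follows the remark that effects may not appear in vivo, but it is tentative and is never called primary.

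Finally, choosing PGE2 as lead is partly a scientific judgement: the central hypothesis works through macrophage phenotype, which is Aim 2. That is a real cost and is counted under the fix.

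**Conclusion.** The inconsistency in Section 3.2 is established from the text alone. The objective sentence and the aim paragraphs disagree on the inflammation score, on impedance and on the microbiome; the Aim 2 primary has two marker definitions; and no ranking across aims resolves this. The consequence is room for selective emphasis and for an optimistic planning estimate. It does not invalidate the trial, but it should be corrected.

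The sizes are illustrative: 11% to 19% for at least one apparently positive primary out of four, and 0.10 to 0.23 SD for the most favourable of four. They rest on no true effect, one reading per aim, 40 per arm for the second figure, and correlations from 0.8 to 0, none of which the documents give except the 40 per arm. They also assume that someone selects by result; the plan states no rule for choosing the next trial's outcome, in either direction.

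**What to change.** In Sections 3.2 and 7.1:

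1. Name one lead estimate: the active-minus-placebo difference in tissue PGE2 at 6 months, with its 95% confidence interval. It is already the Aim 1 primary and is in the objective sentence.
2. State its tissue site. Section 4.3 mentions PGE2 only for the frozen squamous biopsies, while Aim 1 concerns inflammation in Barrett's mucosa.
3. State its form. Section 3.2 speaks of levels and Section 2 of changes; the 6-month value adjusted for baseline is preferable.
4. Rewrite the primary-objective sentence to match.
5. Use one Aim 2 marker list in the aim paragraph, the assay list and Section 7.1.
6. Label the Aim 2 to 4 outcomes, and any Ki-67/caspase staining, as secondary or exploratory, reported as estimates with 95% confidence intervals.

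This is a change of wording; no assay or visit is dropped. The cost is that a favourable finding in Aims 2 to 4 becomes supportive only, including the macrophage measures that are central to the hypothesis. If the sponsor regards those as the better lead, that choice should be made and written down before unblinding.

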#### 4.2 **Exclusion Criteria**

- Allergy to  $\omega$ 3 FFAs, fish or shellfish.
- Presence of high grade dysplasia or cancer on histology.
- Pregnant and or breastfeeding women
- Presence of esophagitis on initial endoscopy or symptoms of refractory GERD (heartburn or regurgitation  $\geq 2$  times a week) indicative of uncontrolled gastroesophageal reflux.
- Inability to give informed consent.
- Currently taking  $\omega$ 3 FFA as prescription.
- Anti-coagulant therapy (Plavix, Warfarin, Coumadin)
- AST or ALT level  $>$  three times upper limit of normal at baseline
- LDL  $> 200$  mg/dl at baseline.
- INR  $> 2$

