#### 4.3 **Subject Recruitment, Enrollment and Screening**

Subjects between 18-85 years of age, with known BE (no dysplasia and low-grade dysplasia) will be identified using an existing GI database for participation in this study. Invitation letters will be mailed to eligible subjects. Subjects will be called to discuss study and scheduled for a screening visit. Subjects taking  $\omega$ 3 FFA as a supplement will discontinue use at least four weeks prior to visit 1. Subjects will report fasting 12 hours for this visit. Subjects meeting inclusion and exclusion criteria will be screened and consented. Baseline assessment will include the measurement of height, weight, waist circumference, hip circumference and waist/hip ratio using standard methods of anthropometric measurements. A comprehensive medication list will be obtained. Patients will also fill out the Reflux Symptom Questionnaire (RSQ)/GER Questionnaire a validated instrument to assess reflux symptoms All patients will continue their baseline PPI regimen to control gastroesophageal reflux. 20cc of blood will be drawn after 12 hours of fasting to obtain a baseline serum FFA profile . Clinical baseline blood will be drawn for inclusion/exclusion: INR, LDL, AST and ALT. Endoscopy will then be performed in a standard manner. Six biopsies will be obtained from the GE junction, and seven biopsies from the BE mucosa 1 cm above the GE junction. Two biopsies from each site will be formalin fixed and paraffin embedded (for inflammatory score assessment) and the remainder frozen at  $-80$  C for subsequent analysis. An additional seven biopsies will be obtained from the squamous mucosa at least 3 cm above the proximal end of the BE segment. Two will be placed in formalin (or other fixative) and paraffin embedded (IHC for macrophage cell counts) and the remainder will be snap frozen at  $-80^{\circ}$  C (PGE2 levels). Endoscopic brushings of the Barrett's segment as well as squamous tissue will be obtained and frozen for each subject. Endoscopic mucosal impedance measurement will be completed during endoscopy. A single slice CT scan of the

abdomen will also be obtained at baseline for each subject to quantify visceral and subcutaneous fat area in the abdomen.

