#### **5.5 Prior and Concomitant Therapy**

A complete list of medications which the patient is currently consuming (both prescription and over the counter) will be obtained at the baseline visit.

Patients currently taking  $\omega$ 3 FFA s as prescription medications will be excluded from the study.

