**Schedule of Events**

Study Activity	Month 0	Month 1	Month 2	Month 3	Month 4	Month 5	Month 6	Month 6 + 7 days
Informed consent	X							
History	X							
Concurrent meds	X							
Physical exam (ht, wt, hip/waist, VS)	X						X	
Blood draw (FFA, LDL, AST, ALT) INR )	X						X	
Endoscopy with bx/brushing and mucosal impedance measurement	X						X	
Randomization	X							
Adverse event evaluation		X	X	X	X	X	X	X
Pill count		X	X	X	X	X	X	
Single slice CT scan of abdomen	X							
Questionnaire	X						X	

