We will align the paired end reads using PANDASeq given our small amplicon size (~392bp) which allows for significant overlap in the two reads. Data will be processed using QIIME1.8.0 (Quantitative Insights Into Microbial Ecology) analysis pipeline. OTUs (Operational Taxonomic Units) will be determined at 97% sequence similarity using uclust, taxonomy will be assigned using RDP classifier against the GreenGenes database, and a phylogenetic tree will be built using FastTree. The OTU table will be rarified at a single sequencing depth. We will compare alpha diversity using both phylogenetic (PD whole tree) and non-phylogenetic measures (Shannon, observed species and Chao1) to assess evenness and richness of distribution. We will compare beta diversity using both phylogenetic (UniFrac) and count based metrics (Bray-Curtis).

Statistical analysis of differences between groups and changes within the microbiome will be performed such as using PERMANOVA to compare beta diversity. Differences in individual taxa between groups will be assessed using ANOVA with correction for multiple hypotheses testing using FDR. A p-value of <0.05 will be considered statistically significant. Additional

analysis to impute potential changes in gene content (PICRUSt) and pathways (HUMANN) will be done depending on the results of initial analysis.

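### Aim 4 measures the esophageal microbiome, but the plan has no rule on recent antibiotic or probiotic use and lists medications only at Month 0, so exposed samples cannot be identified

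*Combined protocol and SAP*

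**What the plan says.** Section 3.2 sets the Aim 4 outcome: "The primary response outcome is the change in the esophageal microbiome in BE subjects following" omega-3 supplementation. Section 2 gives Aim 4 a second task, to describe the microbiome at baseline. Section 3.2 also adds a secondary outcome, the association of the microbiome pattern with waist circumference, waist-hip ratio and visceral fat area. On sampling it says: "The esophageal microbiome will be characterized from biopsies and brushings from the squamous and columnar epithelium using standard methods". Assays are at baseline and six months.

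The drug-related exclusions in section 4.2 are prescription omega-3 and "Anti-coagulant therapy (Plavix, Warfarin, Coumadin"). The same list excludes "Presence of esophagitis on initial endoscopy or symptoms of refractory GERD". The only washout is in sections 4.3 and 6.1, for omega-3 supplements: "FFA as a supplement will discontinue use at least four weeks prior to visit 1". Both sections also keep the baseline PPI regimen unchanged.

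On recording, section 5.5 says: "A complete list of medications which the patient is currently consuming (both prescription and over the counter) will be obtained at the baseline visit". In the Schedule of Events the row "Concurrent meds" is marked at Month 0 and nowhere else.

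The Aim 4 analysis in section 7.1 covers differences between groups and changes within the microbiome, with PERMANOVA for beta diversity. For taxa it says: "Differences in individual taxa between groups will be assessed using ANOVA", with FDR correction. It names no between-arm contrast of change as primary and no covariate for antibiotics or probiotics. The only co-medications handled in the analysis are ASA and NSAIDs, by stratification.

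**The concern.** Aim 4 rests on bacterial 16S sequencing of samples from two endoscopies. Antibiotics and probiotics act on what is being sequenced, yet neither appears in the entry criteria, the concomitant therapy section, the visit procedures, the schedule or the analysis. Elsewhere the plan accepts that co-medication can disturb an outcome: it washes out omega-3 supplements, holds PPI use constant and stratifies on ASA and NSAID use.

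A subject who finished an antibiotic course just before Visit 1 meets every criterion and gives a disturbed baseline sample. Because the list covers drugs in current use, that course need not be recorded. A course shortly before the month-6 endoscopy falls after the only scheduled medication list. The analyst could therefore neither identify the affected samples nor adjust for them.

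Three results are at stake: the baseline description and its association with obesity, any pre-post change reported within an arm, and the precision of the comparison between arms. The last matters because this pilot is meant to supply magnitude and variation for a larger trial.

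**Working it through.** **Inputs from the documents.** 80 completers are planned, 40 per arm (section 3.1), with up to 90 randomised (section 7.1). Allocation is randomised, blinded and placebo-controlled. The plan gives no effect size, SD or power for Aim 4, so there is no figure of its own to reproduce.

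**Assumptions, not in the documents.** A fraction p of each arm is exposed shortly before one endoscopy, unrelated to assignment. Exposure shifts a diversity score by d, in units of the SD of change. The documents support no particular value, so a range is shown.

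**1. Between-arm contrast of change.** Exposure adds variance p(1−p)d². With unit SD and no exposure, the standard error of the arm difference is √(2/40) = 0.224. With exposure it is multiplied by √(1 + p(1−p)d²).

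| p | d | Added variance | SE multiplier | SE |
|---|---|---|---|---|
| 5% | 1 | 0.0475 | 1.023 | 0.229 |
| 10% | 1 | 0.0900 | 1.044 | 0.233 |
| 15% | 1 | 0.1275 | 1.062 | 0.237 |
| 10% | 2 | 0.3600 | 1.166 | 0.261 |

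The SD of the chance imbalance, d√(2p(1−p)/40), is 0.049, 0.067, 0.080 and 0.134 in these rows. It is the same added variance in another form, not a second harm: 0.224² + 0.067² = 0.0547, which is 0.233² up to rounding.

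**2. False-positive rates with no true omega-3 effect.** This is a simulation with 40,000 replicates, 40 per arm, exposure before the month-6 endoscopy only, and two-sided t tests at 0.05. The last column is an exact binomial calculation.

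| p | d | Mean within-arm shift, p×d | Within-arm test | Between-arm test | P(arms differ by 3 or more exposed) |
|---|---|---|---|---|---|
| 5% | 1 | 0.05 | 0.062 | 0.050 | 0.19 |
| 5% | 2 | 0.10 | 0.082 | 0.050 | 0.19 |
| 10% | 1 | 0.10 | 0.088 | 0.051 | 0.35 |
| 10% | 2 | 0.20 | 0.173 | 0.051 | 0.35 |
| 20% | 1 | 0.20 | 0.209 | 0.050 | 0.48 |
| 20% | 2 | 0.40 | 0.480 | 0.050 | 0.48 |

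The between-arm test keeps its level throughout. The within-arm test does not.

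**3. Exposure before both endoscopies.** With fractions p₁ and p₂ the mean within-arm shift is d(p₂ − p₁), which is zero when they are equal. If the two exposures are independent, the added variance is d²[p₁(1−p₁) + p₂(1−p₂)]. For 10% at each visit and d = 1 this is 0.18, and the SE multiplier is √1.18 = 1.086. The mean can cancel; the noise does not.

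**4. Baseline description.** There is no control arm here. With d now in SD of the baseline score, the mean moves by p×d: 0.10 SD at 10% and d = 1, against a standard error of 1/√80 = 0.112 SD. This shift does not shrink with more subjects. For the association with obesity, exposed samples add scatter, and they bias the association if exposure is related to obesity. The documents are silent on that.

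**The case against.** A reader might infer that an antibiotic course would be measured as the omega-3 effect. For the randomised comparison the documents do not support that. There is a blinded placebo arm, section 7.1 plans differences between groups, and courses unrelated to assignment fall on both arms. Simulated between-arm error stays at 0.05, and an ordinary confidence interval already carries the added variance. Section 7.1 makes the same argument about randomisation for ASA. This part of the objection stands in full.

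Other parts also stand. It would be too strong to say that nothing at entry protects Aim 4: excluding esophagitis and uncontrolled reflux and holding PPI use constant help stabilise the mucosa that is sampled. An antibiotic or probiotic in use at Visit 1 should appear on the medication list, which includes over-the-counter products. A steady probiotic user is exposed at both endoscopies, so no later recovery is counted as change. The within-arm inflation above assumes exposure before the second endoscopy only; equal exposure before both would cancel in the mean. Finally, the primary analysis objective in section 3.2 names PGE2, inflammation and macrophage measures, not the microbiome.

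The objection does not reach the baseline description or the obesity association, which have no randomised control. It does not settle within-arm change either, because section 3.2 words the outcome as change following omega-3 and section 7.1 leaves within-microbiome change open. Nor does it supply the missing record: a chance imbalance could be neither seen nor adjusted for.

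**Conclusion.** The concern holds in a limited form. The plan has no rule on recent antibiotic or probiotic use, and its only scheduled medication list is at Month 0. A course completed before Visit 1, or any course before the month-6 endoscopy, can therefore leave no trace in the trial data. This can distort the baseline description, the obesity association and any within-arm change. In the between-arm contrast it adds noise and chance imbalance, not systematic bias.

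The loss of precision is modest over most of the assumed range: the standard error rises by about 2% to 6% for 5% to 15% exposed before one endoscopy at a 1 SD shift, and by about 17% at 10% and 2 SD. Within-arm false positives range from 0.06 to 0.48 for 5% to 20% exposed before the second endoscopy only. All exposure rates and shifts are assumptions, as is independence from assignment. The documents also do not say how long an antibiotic effect lasts in the esophagus. The point affects one of four aims in an estimation pilot, but it is cheap to correct beforehand and cannot be corrected afterwards without the record.

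**What to change.** - **Entry (sections 4.2 and 4.3).** Defer Visit 1 when a subject has had a recent systemic antibiotic course. The investigators should set and justify the window; the four weeks used for omega-3 supplements concerns a different exposure. Deferral comes before randomisation, so it does not disturb the comparison.
- **Probiotics.** Ask steady users to keep their use unchanged between visits, or record any change. Stopping only at entry could create a change of its own if use resumes before month 6.
- **Recording (section 5.5 and Schedule of Events).** Record antibiotic and probiotic use with dates, including recently completed courses, at Visit 1, at the monthly calls and at Visit 2.
- **Analysis (section 7.1).** Name the between-arm contrast of change, with samples from all randomised subjects, as the main Aim 4 estimate. Add a sensitivity analysis that excludes or adjusts for recently exposed samples. Such samples should not be dropped from the main estimate, because that would select on an event after randomisation. Report the baseline description with and without recently exposed subjects.

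The cost is a few delayed Visit 1 bookings and one added question at contacts that already take place. Aims 1 to 3 keep every subject.
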